11.14 Data and Safety Monitoring Board

It is the responsibility of the DSMB to review data quality, relevant safety data, and AEs for all participants enrolled in the study and to make recommendations to the medical monitor, and sponsor regarding the ongoing conduct and monitoring of the study. Details are provided in the DSMB charter.

12 PLANNED STATISTICAL METHODS

12.1 General Considerations

The statistical analyses described in this section will be performed as further outlined in the statistical analysis plan (SAP), which will be finalized prior to database lock. The SAP will supersede the protocol if there are any differences between the two documents in the plans for data analysis and the differences will be noted in the SAP. The SAP will be included as an appendix in the clinical study report for this protocol. Statistical analyses will be performed using SAS 9.2 or higher.

12.2 Determination of Sample Size

For TTSTAND (calculated as a velocity, defined as rise per second), the sample size of 74 participants has been calculated using the following values:

- Mean difference = 0.05
- Standard deviation = 0.075
- Type I error level (two-sided) = 0.05
- Power level = 0.8
- Allocation ratio (N1: viltolarsen/N2: placebo) = 1

The mean difference and the SD were set based on the result of comparison between viltolarsen group and natural history control group at 25 weeks in the Phase 2 Study NS-065/NCNP-01-201 (mean difference between 2 groups: 0.0395, SD: 0.07545 and 0.07377). As the mean difference between the 2 groups at 48 weeks is expected to be larger than at 25 weeks, the mean difference was estimated to be 0.05.

An unpaired t-test for analysis was used instead of mixed effect model repeat measurement (MMRM) for the calculation method due to lack of prior information.

When approximately 90% of participants are enrolled in the study, an unblinded review will be conducted and sample size re-estimation will be considered. An additional unblinded review and re-estimation will be performed when approximately 50 participants have completed the Week 49 evaluations for the primary outcome measure. See [Section 12.8](#) for details.

12.3 Analysis Populations

The safety population will consist of all randomized participants who received at least 1 dose of investigational product. Participants will be analyzed as treated. This will be the primary analysis population for the evaluation of exposure and safety.

The modified Intent-to-Treat (mITT) population will consist of all randomized participants who received at least 1 dose of investigational product and have a baseline assessment and at least 1 post baseline efficacy assessment. Participants will be analyzed as randomized. This will be the primary analysis population for the evaluation of efficacy.

12.4 Demographics and Baseline Characteristics

Summaries of participant demographics (age, race, ethnicity and dominant hand), baseline safety characteristics (anthropometrics, vital signs, physical examination, hematology, chemistry, urinalysis, ECG, and antibodies), and baseline efficacy parameters will be done.

12.5 Efficacy Endpoints

All efficacy analyses will be performed using the modified intent to treat (mITT) population. In addition, additional analyses will utilize the placebo treatment group.

A hierarchical analysis, following a fixed-sequence hypothesis testing method, is used to first test TTSTAND and then TTRW, 6MWT, NSAA, TTCLIMB, and hand-held dynamometer, if the former was statistically significant.

12.5.1 Efficacy Objective

The primary efficacy outcome measure (TTSTAND) will be summarized by treatment group over time using descriptive statistics.

The TTSTAND times to perform the test will also be converted to velocities. Note that a test result that is to be converted to velocity that the participant could not perform due to disease progression will have velocity set to zero only at the first visit where this occurs. After that visit, missing observations due to disease progression will be left as missing.

The TTSTAND will be compared between the viltolarsen treated participants and the placebo treated participants using MMRM analysis with treatment group, week of the visit, and the treatment-by-week interaction as factors, and age as one covariate, and baseline performance as a second covariate. The TTSTAND times to perform the test will be converted to velocities.

The treatment comparisons of most interest will be the LS means contrasts between the viltolarsen treated participants and the placebo treated participants at Week 49.

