	
Efficacy Evaluation:
 
The primary efficacy outcome of TTSTAND will be summarized descriptively at each visit using actual values and change from baseline values. The time measured for TTSTAND will be converted to a velocity expressed as rise per second.
 
The primary efficacy outcome measure of TTSTAND velocity will be compared between participants treated with viltolarsen or placebo using mixed-effects linear models.
 
Secondary and exploratory outcomes are detailed in the protocol and statistical analysis plan.
 
Safety Evaluation:
 
Safety analyses will be performed using the safety population. All safety assessments will be based on actual treatments received by participants and are detailed in the protocol and statistical analysis plan.
 
Pharmacokinetic Evaluation:
 
Population PK analysis will be presented in a separate report.

--	--

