5.2 Design Implementation

5.2.1 Randomization

Participants are randomly assigned to either 80 mg/kg/week viltolarsen or placebo in a 1:1 ratio. Randomization is carried out with dynamic allocation by minimization method with the biased-coin method. The allocation factors are gene mutation and baseline values for TTSTAND, and region (North America, South America, European Union [EU], and Asia). [REDACTED]

[REDACTED]

The randomization schedule will be generated by an unblinded statistician and maintained by the contract manufacturing organization (CMO). All other parties will be blinded to the randomization.

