12.5.2.2 Analysis Comparing Viltolarsen to Placebo

TTSTAND, TTRW, 6MWT, NSAA, TTCLIMB, and hand-held dynamometer results will be compared between the viltolarsen treated participants and the placebo treated participants using MMRM analysis with treatment group, week of the visit, and the treatment-by-week interaction as factors, and age as one covariate, and baseline performance as a second covariate. The TTRW and TTCLIMB times to perform the test will be converted to velocities. For a test that the participant could not perform, the velocity will be set to zero.

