12.8 Interim Analyses

Interim analysis is planned when approximately 90% of participants are enrolled in the study. An additional unblinded review and re-estimation will be performed when approximately 50 participants have completed the Week 49 evaluations for the primary outcome measure. At these 2 time points, an unblinded data review will be conducted, which will include review by the DSMB. Based on this review, the DSMB will make a recommendation to the sponsor for possible sample size re-estimation, i.e., the additional number of participants to be enrolled to increase the conditional power to an acceptable level.

Denne (Denne, 2001) described the sample size re-estimation procedure for the group sequential test by using the conditional power without inflating the type I error rate for the interim analyses. At the point at which the sample size re-estimation is being made for the interim analyses, the test statistic z_1 is observed. The conditional power is the probability of rejection H_0 on the basis that $Z_2 \geq c_2$ given $Z_1 = z_1$, which is denoted by $CP_\theta(n_2, c_2|z_1)$. The conditional power is given by:

$$CP_\theta(n_2, c_2|z_1) = 1 - \Phi \left[\frac{c_2\sqrt{n_2} - z_1\sqrt{n_1} - \frac{(n_2-n_1)}{\sqrt{2}\sigma^2}\theta}{\sqrt{n_2 - n_1}} \right]$$

where n_1 is the sample size per treatment group at the interim analyses, the true difference in mean response θ is estimated by the current sample mean difference δ , and σ^2 is estimated by the current sample within group variance s^2 . The re-estimated sample size per treatment group n_2 is obtained by solving the conditional power be at least 80% power as defined in the sample size determination. The re-estimated total sample size is given by $n^* = 2n_2$.

To preserve study integrity, a small alpha of 0.001 will be spent at the second re-estimation resulting in the overall significance level to be 0.049 at the final stage.

If the re-estimated total sample size from the interim analyses is smaller than the planned total sample size of 74, the sample size adjustment will not be needed. If the re-estimated total

sample size is larger than the planned total sample size, the sample size may be increased up to a maximum target sample size of 100.

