12.9 Handling of Missing Data

Every effort will be made to collect all data. However, despite best efforts, missing or incomplete data may be reported. All missing or partial data will be presented in the participant data listing, as they are recorded on the eCRF.

Participants lost to follow-up or withdrawn will be included in statistical analyses up to the point of their last evaluation. Unless otherwise specified, no imputation of values for missing data will be performed. Of note, since participants with DMD are expected to decline over time, imputing efficacy parameters by last value carried forward mostly biases towards participants appearing stronger or faster than they are, since it carries forward potentially a better value than the value at the time of the missed observation. Therefore, for this study, we will summarize how much data are missing, but do not expect to need to impute any data to accomplish the analyses as described. Details of handling missing data will be described in the SAP.

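### The MMRMs omit gene mutation and region, two of the three minimisation factors, without a stated reason; if these factors are prognostic, the Week 49 test is conservative and some power is forgone

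*Combined protocol and SAP*

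**What the plan says.** Section 5.2.1 assigns participants 1:1 by minimisation with a biased coin: "The allocation factors are gene mutation and baseline values for TTSTAND, and region (North America, South America, European Union [EU], and Asia". Some text directly after this sentence is redacted.

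Section 12.5.1 analyses TTSTAND velocity "using MMRM analysis with treatment group, week of the visit, and the treatment-by-week interaction as factors, and age as one covariate"; the second covariate is baseline performance. The result of interest is the set of "LS means contrasts between the viltolarsen treated participants and the placebo treated participants at Week 49". Section 12.5.2.2 repeats the model for the other function and strength endpoints, again with treatment, week and their interaction "as factors, and age as one covariate, and baseline performance as a second covariate".

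The synopsis is less specific and names no covariates: "The primary efficacy outcome measure of TTSTAND velocity will be compared between participants treated with viltolarsen or placebo using mixed-effects linear models". Section 12.1 sends further detail to a SAP that prevails over the protocol where they differ; no separate SAP text is in the supplied document.

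Two other sections bear on the size of the point. In 12.2, "An unpaired t-test for analysis was used instead of mixed effect model repeat measurement (MMRM) for the calculation method". In 12.8, the final test is at 0.049 and "the sample size may be increased up to a maximum target sample size of 100".

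**The concern.** For TTSTAND, the baseline covariate covers one of the three allocation factors. The other two, gene mutation and region, are balanced by design and then left out of the analysis.

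Minimisation removes most of the chance imbalance in these factors, so any effect they have on outcome largely drops out of the true variance of the treatment contrast. A model without them still counts that variance as error. Its standard error is then too large, its confidence interval too wide, and its test rejects less often than its nominal level.

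What is at stake is precision that the design has already secured. This matters more in a trial that may enrol up to 26 further boys (100 − 74) to raise conditional power, and in which TTSTAND stands first in the fixed sequence of 12.5, so that a missed primary result blocks every secondary test.

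**Working it through.** **Inputs from the protocol.** Difference 0.05, SD 0.075, two-sided 0.05, power 0.8, 1:1 allocation (12.2); final-stage level 0.049 (12.8).

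**The plan's own figure.** With an exact noncentral t, 37 per arm gives power 0.808 and 36 gives 0.797, so N = 74 is reproduced. At 0.049, power at N = 74 is 80.5%.

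**Inputs that must be assumed.** R2 is the share of Week 49 residual variance that mutation and region explain beyond age and baseline. The documents give no value. The four region levels are printed in 5.2.1; the mutation levels, the shares in each level and the coin probability are not visible.

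**Step 1: limiting case of perfect balance, normal theory, level 0.049.** The critical value is 1.969. The noncentrality is 0.05 / (0.075 × √(2/37)) = 2.867.

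- Null rejection, factors omitted: 2[1 − Φ(1.969/√(1 − R2))] = 4.3%, 3.8% and 2.8% at R2 = 0.05, 0.10 and 0.20.
- Power, factors omitted: 1 − Φ((1.969 − 2.867)/√(1 − R2)) = 82.8% at R2 = 0.10 and 84.3% at 0.20.
- Power, factors included: 1 − Φ(1.969 − 2.867/√(1 − R2)) = 85.4% and 89.2%.
- Gain: 2.6 and 4.9 points.

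**Step 2: simulation of the planned analysis.** Four-visit unstructured REML MMRM (Weeks 13, 25, 37, 49), N = 74, complete data, level 0.049, 40,000 replicates per scenario. Assumed: coin 0.8; two baseline classes; mutation shares 0.40/0.35/0.25; region shares 0.35/0.10/0.30/0.25; R2 split equally between the two factors; visit correlation 0.8 per step. The power columns are for three mutation groups, main effects and factor effects constant over visits. The null-rejection ranges span the scenarios run.

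| R2 | Null rejection as planned (%) | Power as planned (%) | Power with both factors (%) | Change (points) |
|---|---|---|---|---|
| 0 | 4.8–4.9 | 80.2 | 79.6 | −0.6 |
| 0.05 | 4.4–4.7 | 80.4 | 81.4 | +1.0 |
| 0.10 | 3.9–4.1 | 81.0 | 83.5 | +2.5 |
| 0.20 | 3.0–3.6 | 81.7 | 87.5 | +5.8 |

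The simulated null rejection lies between the Step 1 limit and nominal, as imperfect biased-coin balance should produce. A separate single-visit ANCOVA simulation at 0.05, with equally likely levels, agrees: null rejection 4.1% and 3.2% as planned at R2 = 0.10 and 0.20, and power gains of 2.5 and 5.0 points.

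**Step 3: sensitivity of the main-effects gain (R2 = 0.10 / 0.20).**

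- Three groups, factor effects rising over visits: +2.2 / +4.7.
- Seven mutations with sparse levels pooled, constant effects: +2.0 / +4.5.
- Seven pooled, rising effects: +1.4 / +3.6.
- Residual SD also rising over visits: +0.8 / +1.9 (three groups) and +0.5 / +1.5 (seven pooled).

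**Step 4: break-even.** With factor-by-week terms, interpolation puts break-even at an R2 of about 0.025 (three groups) and 0.045 (seven pooled). For main effects it is somewhat lower. Three groups: −0.6 at R2 = 0 and +0.1 at 0.02 give 0.02 × 0.6/0.7 ≈ 0.017. Seven pooled: −1.0 at 0 and +0.6 at 0.05 give 0.05 × 1.0/1.6 ≈ 0.031. Below break-even the change is a loss.

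**Step 5: the gain in participants.** Unadjusted t-test power at 0.049 is 80.5% at N = 74, 82.6% at 78, 83.5% at 80 and 86.9% at 88. A gain of 2.5 points (to 83.0%) falls near N = 79, about 5 more participants. A gain of 5.8 points (to 86.3%) falls near N = 87, about 13 more.

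**The case against.** **The size is all assumption.** This stands. R2, the mutation groups, the level shares and the coin probability are not in the visible text. Section 2.1.3 names TTSTAND itself as the prognostic factor, and its baseline is already in the primary model together with age. At R2 = 0.05 the gain is about 1 point or less, and nothing in the documents shows on which side of break-even this trial lies.

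**The SAP or the redacted text may settle it.** Possibly. The point is therefore limited to the model that the protocol states, which leaves out two of its own allocation factors.

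**Complete data only.** This also stands. Section 12.5.1 leaves velocities missing after the first zero and 10.4 bars replacement, so the simulated figures are approximate.

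**Stronger readings that the documents do not support.**

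- A reader might infer inflated type I error. The direction is the opposite: null rejection is at or below nominal in every scenario.
- A reader might infer that the trial is underpowered. It is not on this account: N = 74 comes from an unadjusted t-test, and simulated power as planned stays at about 80% or above.
- A reader might hold that factor-by-week terms are needed, because the contrast is at Week 49 and "since participants with DMD are expected to decline over time", and that main effects would recover under half of the gain. That holds only if residual SD also rises over visits (three groups, R2 = 0.10: 0.8/2.2 = 36%). With constant effects main effects recover the whole gain (2.5 against 2.1), and with rising effects 2.2/2.5 = 88%. The rising-SD scenario implies a Week 25 SD of 0.6 × 0.075 = 0.045, whereas 12.2 reports 0.07545 and 0.07377 at 25 weeks and carries 0.075 forward. The protocol does not say whether those are residual SDs, but they give no support to a steep rise.

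**Conclusion.** The concern holds as a matter of efficiency and calibration. The protocol minimises on three factors and adjusts for one of them, plus age, without saying why.

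If mutation and region explain 10% or 20% of residual variance, null rejection at Week 49 is about 4% or 3% against 4.9%, and roughly 2 to 3 or 5 to 6 points of power are forgone. The gain is smaller with more mutation levels, or if factor effects and residual SD rise over visits. If the factors explain almost nothing, adding them costs a little power, at most about 1 point.

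The direction follows from the design. The size rests on an unknown R2, assumed level shares and coin probability, and complete data. Low to moderate priority: worth changing because it is cheap, not because the planned test is invalid.

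**What to change.** In 12.5.1, 12.5.2.2 and the SAP:

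- Add gene mutation group and region as fixed effects, at the levels used in the minimisation.
- Pool sparse levels (for example, fewer than 8 participants counted over both arms) by a rule fixed before the first unblinded review.
- State which region level Oceania sites fall in. The synopsis and 5.1.1 list Oceania among the recruiting regions; the visible list in 5.2.1 does not.
- Treat factor-by-week terms as optional, for example as a sensitivity analysis.
- If the factors are left out on purpose, give the reason.
- Optionally, say what baseline performance means in the secondary models. If it is each endpoint's own baseline, baseline TTSTAND is also missing there.

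The cost is wording only, with no new data. With three mutation groups and four regions the model uses 2 + 3 = 5 more between-participant degrees of freedom (about 6 with seven mutations pooled). If neither factor is prognostic, the main-effects model loses 0.2 to 1.0 points of power.

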2.2.3 Glucocorticoid Treatment

At present, treatment with glucocorticoid (GC) medication is the only pharmacological intervention that has been shown to slow the decline of strength and function in DMD patients. The two main GCs used in DMD are prednisone and deflazacort (EMFLAZA™). Daily oral administration of prednisone or deflazacort stabilizes or improves strength and prolongs ambulation (Drachman et al, 1974; Brooke et al, 1987; Griggs et al, 1993; Mendell et al, 1989; Griggs et al, 1991; Fenichel et al, 1991). The mechanism by which GCs are beneficial in dystrophin deficiency is likely multifactorial, including anti-inflammatory actions. The immunosuppressive effects of GCs may not be beneficial, and other immunosuppressants have not shown benefit (Griggs et al, 1993). On February 9, 2017, the US FDA approved EMFLAZA™ for the treatment of patients 5 years of age and older with DMD.

In 2005, the American Academy of Neurology issued a practice parameter regarding GC treatment in DMD and recommended that GC should be offered as treatment, despite known side effects (Moxley et al, 2005). The significant side effects of GCs include Cushingoid features, adverse behavioral changes, obesity, growth retardation, increased risk for bone fractures, gastritis, delayed puberty, cataracts, hypertension, glucose intolerance, susceptibility to infection, and masking of response to stress (Matthews et al, 2016).

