8 PRIOR AND CONCOMITANT MEDICATIONS AND TREATMENTS

Glucocorticoid steroids and other pharmacological medications including over the counter medications, herbal remedies, supplements, and vitamins used within 3 months prior to the first dose of study drug will be recorded in source documents and in the electronic case report form (eCRF). The date of first glucocorticoid steroid use will also be captured. All medications taken throughout the study will be recorded in source documents and in the eCRF. The following information will be collected: the medication name, dose, unit, frequency, route, indication, start and stop dates.

Any non-pharmacological treatment the participant has received within 3 months prior to the first dose of study drug will be collected. The following information will be collected: name of treatment, indication, and start and stop date. Prior non-pharmacologic treatment will be recorded in source documents and captured in the relevant eCRF. Physical therapy schedule should not change, and no new physical therapy should be started during the study. The need for changes to physical therapy should be discussed with the medical monitor prior to implementation.

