8.1 Prohibited Medications

Investigators are reminded to minimize concomitant medication or supplement use or changes to GC steroid use unless necessary for medical management.

The use of idebenone, anabolic steroids (e.g., oxandrolone), and products containing resveratrol or adenosine triphosphate is prohibited from 3 months prior to first dose of study drug and through the duration of the study. If growth hormones or supplements with a potential effect on muscle strength or function (e.g., coenzyme Q10 or creatine) are used, these should be kept stable from 3 months prior to the first dose of study drug through the duration of the study. Adjustments based on changes in body habitus are permitted. Any other experimental/investigational products are prohibited from 3 months prior to first dose of study drug or within 5 times the half-life of a medication, whichever is longer. Any other exon skipping agents and any gene therapies are prohibited. Participants who begin another investigational product will be withdrawn from the study.

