8.2 Allowable Medications

Investigators may prescribe concomitant medications or treatments deemed necessary to provide adequate therapeutic and supportive care. Specifically, participants should receive full medical care during the study, including transfusions of blood and blood products, treatments with antibiotics, anti-emetics, anti-diarrheals, analgesics, topical or inhaled steroids, and other care as usual. All concomitant blood products, medications, and supplements will be recorded in source documents and in the relevant eCRF. For a stable dose of glucocorticoid, a stable dose permits weight-based adjustments (stable mg/kg).

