12.6.3 Concomitant Medications and/or Other Treatments

Glucocorticoids, which are required as part of the inclusion criteria, will be summarized by type of GC (prednisone vs. deflazacort), by schedule (daily vs. any other), and by treatment.

Participants are required not to change the GC dose while on study. Any changes in doses or schedule will be listed.

Other concomitant medications will be summarized by ATC class and preferred term. Each medication will be counted once within a participant using it, regardless of the number of times it was reported on the eCRFs. The summaries will note new medications or supplements vs. those already given at baseline and study entry. Any other treatment, surgeries, will be listed and described; however, those are expected to be few without a need to be summarized using tables.

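### Baseline glucocorticoid regimen is recorded but left out of the efficacy model, and on-study glucocorticoid changes are only listed, under rules that conflict

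*Combined protocol and SAP*

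**What the plan says.** Protocol section 2.2.3 calls GC treatment "the only pharmacological intervention that has been shown to slow the decline of strength and function in DMD patients". Inclusion criterion 7 requires a GC dose that has been stable for at least 3 months. It fixes neither drug nor schedule.

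Section 8 records GC name, dose and frequency, and adds: "The date of first glucocorticoid steroid use will also be captured". Section 12.6.3 tabulates GC by treatment arm, by type (prednisone or deflazacort) and by schedule (daily or any other).

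None of this is used further in the visible text. On randomisation, section 5.2.1 states: "The allocation factors are gene mutation and baseline values for TTSTAND, and region"; what follows the list of regions is redacted. The primary MMRM in 12.5.1 has "treatment group, week of the visit, and the treatment-by-week interaction as factors, and age as one covariate, and baseline performance as a second covariate", and 12.5.2.2 gives the same terms for the secondary endpoints.

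Three sections deal with GC changes during the study:

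- 8.1 asks investigators to minimise "changes to GC steroid use unless necessary for medical management".
- 8.2 says that "a stable dose permits weight-based adjustments (stable mg/kg".
- 12.6.3 says: "Participants are required not to change the GC dose while on study. Any changes in doses or schedule will be listed".

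Section 12.1 says that a separate SAP will supersede the protocol where they differ. That SAP is not in the supplied document.

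**The concern.** The protocol treats GC as effective background therapy and already defines regimen categories, yet makes no analytic use of them. With 37 boys per arm, regimens can differ between arms by chance. Baseline TTSTAND and age absorb part of a regimen's effect, but not any part that shows only in the later slope. If an imbalance is noticed in the by-arm table, adjusting for it then would be post hoc.

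The second gap is after baseline. Boys aged 4 to under 8 gain weight over 48 weeks, so a constant mg/kg dose implies a changing dose in mg. A listing of every dose change therefore mixes weight adjustments with real changes of mg/kg or schedule. The visible plan has no by-arm summary of such changes, no estimand strategy for them and no sensitivity analysis. What is at stake is some power, and the ability to show that the Week 49 result does not depend on GC changes.

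**Working it through.** **1. The plan's own figure.** Inputs from section 12.2: difference 0.05, SD 0.075, two-sided alpha 0.05, power 0.80, 1:1, unpaired t-test. Non-central t with non-centrality 0.05/(0.075 x sqrt(2/n)) and 2n - 2 df gives power 0.797 at n = 36 and 0.808 at n = 37. So "the sample size of 74 participants has been calculated using the following values" reproduces at 37 per arm. At the final alpha of 0.049 (section 12.8) power is 0.805. The SE of the contrast is 0.075 x sqrt(2/37) = 0.0174.

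**2. Does omitting a baseline GC term bias the test?** 100,000 trials were simulated with no drug effect, simple randomisation, half the boys on each of two regimens, and a regimen difference of 0.05 or 0.075 rise/s. The unadjusted t-test at 0.05 rejected in 0.0498 and 0.0504 of trials, with mean estimated difference about zero. There is no systematic bias and no inflation.

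**3. Chance imbalance.** The documents give neither the regimen mix nor a regimen effect. Assume a share p = 0.3 to 0.4 not on daily GC, and a Week 49 difference g = 0.02 to 0.05 rise/s between regimens beyond age and baseline.

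- Exact binomial chance of a gap of at least 15 points between arms, in either direction: 0.162 at p = 0.3 and 0.191 at p = 0.4.
- Shift at a 15-point gap: 0.15 x g = 0.003 to 0.0075. That is 6% to 15% of the planned 0.05, and 0.17 to 0.43 of the SE.
- Wider ranges (p = 0.2 to 0.5, g = 0.02 to 0.075): the 95% limits of the gap, 1.96 x sqrt(2p(1-p)/37), are 18.2 to 22.8 points. The shift at those limits is 0.0036 to 0.0171, or 7% to 34% of 0.05.

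**4. Precision.** Share of variance removed: R² = p(1-p)g²/0.075². Power is at alpha 0.049 with SD 0.075 x sqrt(1-R²).

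| p | g | R² | Residual SD | Power |
|---|---|---|---|---|
| no adjustment | - | 0 | 0.0750 | 0.805 |
| 0.3 | 0.02 | 0.015 | 0.0744 | 0.811 |
| 0.4 | 0.05 | 0.107 | 0.0709 | 0.847 |

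Taking off 2 df leaves 0.811 and 0.847 unchanged to three decimals.

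**5. On-study changes.** Consider a boy who gains weight and whose dose in mg is raised to hold mg/kg. He is stable under 8.2, but has changed his GC dose under the wording of 12.6.3. A boy whose GC is changed for medical management is tolerated by 8.1 and ruled out by 12.6.3. Both appear in the same listing.

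For scale only, suppose the share with a real change differs between arms by 5 to 20 points and a change is worth 0.02 to 0.075 rise/s. The contrast then moves by 0.05 x 0.02 = 0.001 up to 0.20 x 0.075 = 0.015. At alpha 0.05, an unfavourable shift lowers power from 0.808 to between 0.79 and 0.51. With no drug effect, the rejection rate would be 0.050 to 0.136. All of this requires changes that differ by arm.

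**The case against.** The strongest reply is that randomisation already deals with baseline GC. Chance imbalance is part of the standard error, and step 2 confirms that the test keeps its level. This stands. A reader might infer that GC differences feed systematically into the Week 49 contrast, or that a material imbalance is likely. The documents support neither: a gap of 15 points or more has a 16-19% chance even under the assumed mix, and only about half of that is unfavourable.

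Second, section 2.2.3 says that GC works, and every boy must be on it. It describes benefit from daily prednisone or deflazacort, but does not compare daily with other schedules, one drug with the other, or short with long use. This also stands. The regimen effects above are assumptions, and the upper value of 0.05 equals the whole planned drug effect.

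Third, baseline TTSTAND is both an allocation factor and a covariate, age is a covariate, and 12.6.3 would make a baseline imbalance visible. That reduces the concern, but visibility is not adjustment.

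Fourth, 8.2 can be read as defining what the other sections mean by a stable dose, which would leave 8.1 against 12.6.3 as the main conflict. That reading is reasonable, but 12.6.3 does not say so, and its listing still covers any dose change. Dose, dates and weight are recorded, so the two kinds of change could be separated; the plan does not say that they will be.

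Finally, a reader might infer that GC is changed more often in the arm declining faster, which would mask a drug effect. No figure in the documents shows this, and a baseline covariate would not address it.

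**Conclusion.** The point holds as two modest improvements, not as a flaw that threatens the validity of the primary test.

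- **Baseline regimen.** Leaving it out costs some precision and leaves chance imbalance uncorrected. Under the assumptions in step 3, power would rise from 0.805 to about 0.81-0.85; the lower end is negligible. The figures treat 0.075 as the residual SD, and assume that the GC term captures the full Week 49 difference.
- **On-study changes.** The rules in 8.1, 8.2 and 12.6.3 conflict, and the visible plan provides only a listing. The shift of 0.001 to 0.015 is illustrative, since the documents give no rate of change by arm.

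Statements about what is absent apply to the visible protocol only. If the SAP or the redacted randomisation text covers GC, the corresponding part falls. The conflict between the three sections would remain in the protocol.

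**What to change.** **Baseline (free improvement).** Before any further unblinded review, add baseline GC schedule (daily or other) to the MMRM in 12.5.1 and 12.5.2.2. Add GC type as well if the categories are large enough, using those already defined in 12.6.3. State in advance how small categories are pooled and whether the term is crossed with week. No new data are needed. The cost is 1-2 df out of 72, or slightly more in the repeated-measures model if the term is crossed with week.

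**On-study changes (cheap improvement).**

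- Reconcile 8.1, 8.2 and 12.6.3 so that one definition of a GC change is used throughout. This point takes no view on which rule is right.
- Replace the bare listing with a by-arm summary that separates weight-only adjustments at stable mg/kg from changes of mg/kg or schedule.
- Keep the treatment-policy analysis, which uses TTSTAND regardless of GC change, as primary. Add one sensitivity MMRM with a named strategy. One example is a hypothetical strategy that sets TTSTAND to missing after a change of mg/kg or schedule, with the missing-at-random assumption stated.

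The cost is SAP wording, one table and one extra model run.
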